7.1.1.2 Other Events of Special Interest

Other events of special interest (OEOSI) consist of a list of preferred terms grouped by specific category (e.g. Myositis Event, Myocarditis Event, Demyelination Event, Guillain-Barre Syndrome, Pancreatitis Event, Uveitis Event, Encephalitis Event, Myasthenic Syndrome, Rhabdomyolysis Event, Graft Versus Host Disease). The list of MedDRA preferred terms used to identify OEOSI is revisited quarterly and updated accordingly. The preferred terms used for the selection at the time of the database lock by categories will be provided.

7.1.1.3 Immune-Mediated Adverse Events

In order to further characterize AEs of special clinical interest analysis of immune-mediated AEs (IMAE) will be conducted. Immune-mediated AEs are specific events (or groups of PTs describing specific events) that include pneumonitis, diarrhea/colitis, hepatitis, nephritis/renal dysfunction, rash, endocrine (adrenal insufficiency, hypothyroidism/thyroiditis, hyperthyroidism, diabetes mellitus, and hypophysitis), and other specific events, considered as potential immune-mediated events by investigator, that meet the definition summarized below:

- those occurring within 100 days of the last dose,
- regardless of causality,
- treated with immune-modulating medication (of note, endocrine AEs such as adrenal insufficiency, hypothyroidism/thyroiditis, hyperthyroidism, diabetes mellitus, and hypophysitis are considered IMAEs regardless of immune-modulating medication use, since endocrine drug reactions are often managed without immune-modulating medication).
- with no clear alternate etiology based on investigator assessment, or with an immune-mediated component

The list of MedDRA preferred terms used to identify Immune-Mediated adverse events is revisited quarterly and updated accordingly. The preferred terms used for the selection at the time of the database lock by categories will be provided.

7.1.2 Laboratory Tests

Clinical laboratory parameters (hematology, serum chemistry and electrolytes) will be evaluated.

Laboratory tests will be graded using the NCI Common Terminology Criteria, and the most recent version of the criteria at the time of the database lock will be used.

Clinical laboratory data will be first analyzed using International System of Units (SI).

Analyses will be repeated using US conventional units.

In the laboratory summary tables, unless otherwise specified, subjects will be counted only once for each lab parameter according to their worst on treatment CTC grade (worst being the highest CTC grade). The laboratory tables and listings will be sorted by laboratory category, laboratory sub-category and laboratory test code sequence number.

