4.5.1 Nivolumab Dosing

4.5.1.1 Nivolumab Dose and Schedule

Subjects randomized to nivolumab should begin treatment within 7 days of randomization, but RT should begin within 42 days after definitive resection, but may be delayed if clinically required. Subjects will continue on study treatment until progression, unacceptable toxicity, withdrawal of consent, or the study ends, whichever comes first.

Subjects randomized to the RT + nivolumab arm will begin nivolumab at a dose of 240 mg, given as a 30-minute IV infusion on Day 1 of each treatment cycle Q2W for 8 doses. The nivolumab dose will then change to 480 mg as a 30-minute IV infusion Q4W with dose 9 (starting week 17, in the absence of delays). Nivolumab injection can be infused undiluted or diluted so as not to exceed a total infusion volume of 120 mL. Nivolumab infusion must be promptly followed by a saline flush to clear the line.

Continuation of nivolumab treatment with suspected progression is permitted, see Section 4.5.1.6. Treatment will continue until discontinuation from study treatment for any of the criteria listed in sections 3.5 or 4.5.1.5.

There will be no dose escalations or reductions of nivolumab allowed. Subjects may be dosed no less than 12 days from the previous dose during Q2W cycles. A dose given more than 3 days after the intended dose will be considered a delay. For Q4W dosing cycles, subjects may be dosed within a ± 3 day window. Premedications are not recommended for the first dose of nivolumab.

Subjects should be monitored for infusion reactions during nivolumab administration. If an acute reaction is noted, subjects should be managed according to [Section 4.5.1.8](#).

Doses of nivolumab may be interrupted, delayed or discontinued depending on how well the subject tolerates treatment. Dosing visits are not skipped, only delayed. Nivolumab should be delayed (see [Section 4.5.1.3](#)) for toxicities considered at least possibly-related to nivolumab. Nivolumab interruption refers to stopping the infusion, eg, for an infusion reaction (see [Section 4.5.1.8](#)).

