4.5.2 Temozolomide Dosing

4.5.2.1 Temozolomide Dose and Schedule

Subjects on RT + TMZ will be administered temozolomide (TMZ, Temodar[®]) daily during RT and as maintenance therapy for 6 cycles. TMZ dosing will be performed according to institutional standard; the following guidance is drawn from published literature.

Temozolomide (TMZ) will be dosed at 75 mg/m² once per day continuously throughout RT, typically for 42 days and with a maximum of 49 days. See [Table 4.5.2.3-1](#) for dose modifications during concomitant RT + TMZ dosing. After completion of RT, there will be a 4-week break. Subjects will receive 6 cycles of temozolomide daily x 5 days every 28 days.

Dose Level	TMZ Dose in mg/m²/day	Notes
-1	100 mg/m ² /day	Reduction for prior toxicity
0	150 mg/m ² /day	Dose during Cycle 1
1	200 mg/m ² /day	Dose during C2-6 in absence of TMZ-related toxicity

Source: adapted from Temodar[®] package insert (PI)

In the first maintenance cycle TMZ is given at a dose of 150 mg/m², and then increased to 200 mg/m² in cycle 2 as follows: If, during the first cycle, all non-hematologic AEs observed were grade ≤ 2 (except alopecia, nausea and vomiting) and with platelets ≥ 100 x 10⁹/L and ANC ≥ 1.5 x 10⁹/L, then the temozolomide dose should be escalated to dose level 1 and this dose should be used as the starting dose for subsequent cycles. Doses of TMZ are not precise but are adjusted based on tolerance; rounding of up to 10% is entirely acceptable.

If treatment after cycle 1 has to be delayed because of ongoing non-hematologic AEs of grade ≥ 2, then no escalation is possible. If the dose was not escalated at Cycle 2, then the dose should not be escalated in further cycles based on AEs (see [Table 4.5.2.3-2](#)). If there was a prior dose reduction during the concomitant period with RT, then dose -1 should be the starting dose for subsequent cycles. Table 4.5.2.1-1 describes dose levels during temozolomide monotherapy.

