Targeted Physical Examination, Vital Signs	Q2 wks	Day 1 of each cycle	Q2 wks x 8 doses, then Q4 wks	Weight, BP, HR, RR, temperature, and Karnofsky Performance Status
Adverse Events Assessment	Continuously			Record at each visit
Review of Concomitant Medications	X	X	X	Record at each visit, including steroid dose
Radiation Therapy	See Note		See Note	Total dose 60 Gy over 6-7 weeks, see Section 3.1.2.2
CBC with Differential	Weekly	Day1&22 of each cycle	Within 3 days prior to each dose	Weekly if delayed and as clinically indicated
Chemistry panel	Q4 wks	Day 1 each cycle	Within 3 days prior to each dose	Chemistry panel: AST, ALT, ALP, T.Bili, albumin, BUN or serum urea, creatinine, Ca, Na, K, Cl, LDH, Glucose Additional tests, as clinically indicated, will also be submitted
Thyroid Function Test		X	X	TSH every 8 weeks, T3 and T4 (Free or Total, if TSH abnormal) and as clinically indicated
Pregnancy Test [WOCBP only]	Every 4 weeks			Serum or urine pregnancy test every 4 weeks (± 3 days; minimum sensitivity 25 IU/L or equivalent units of HCG).
				
Tumor Assessment	X (See Note)			Contrast-enhanced MRI 4 weeks (± 7 days) after completing RT, then every 8 weeks (± 7 days) ^a until progression. See Section 5.4.1
				

Table 5.1-2: On-Treatment Assessments (CA209498)

Procedure	RT + TMZ	TMZ Maintenance	RT + Nivolumab	Notes: Windows refer to calendar days. Procedures must be done within 72h prior to dosing unless otherwise specified.
[REDACTED]		[REDACTED]		[REDACTED]
[REDACTED]		[REDACTED]		[REDACTED]
[REDACTED]		[REDACTED]		[REDACTED]
Health Care Resource Utilization		X (See Note)		Obtained prior to dosing Day 1 Week 1 and then with each MRI, (± 7 days) see Section 5.8.4
[REDACTED]		[REDACTED]		[REDACTED]
Dispense Nivolumab			X (see note)	Day 1 within 7 days of randomization, then every 2 weeks for 8 doses, then every 4 weeks
Dispense Temozolomide	D1, D15, D29 & D43 (if needed)	D1 each cycle		Temozolomide taken daily during RT then 4 week break, then daily x 5 in 28-day cycles x 6 cycles, see Section 4.5.2
Tumor Sample at time of progression or suspected progression	At time of PD or suspected PD			If biopsy or surgical resection is performed at progression or suspected progression, a tumor sample (block or slides) should be submitted for central neuropathologic review
Assess Temozolomide Compliance	X	X		Review medication diary

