^a Per RANO, assessment of disease progression during study requires that MRI scan be performed >12 weeks after RT; it is, therefore, recommended that second on-treatment scan be performed at least 84 days after completion of RT.

Table 5.1-3: Treatment Follow-up and Survival Follow-Up (CA209-498)

Procedure	Treatment Follow-up ^a	Survival Follow-up ^b	Notes
TIMING	35 and 115 days (±7 Days) after last dose	Q 3 Months (± 14 Days)	
Targeted Physical Examination	X		Weight, BP, HR, RR, temperature and Karnofsky Performance Status
Adverse Events Assessment	X	X	Beyond 100 days from the last dose of study treatment subjects will be followed for ongoing drug-related adverse events until resolved, return to baseline or deemed irreversible or until lost to follow-up or withdrawal of study consent
Laboratory Tests	X		CBC w/differential, LFTs, BUN, creatinine and TSH at 35 days, repeat labs at 115 day visit if study drug-related toxicity persists.
Pregnancy Test [WOCBP only]	X		Serum or urine pregnancy test (minimum sensitivity 25 IU/L or equivalent units of HCG).
Review of Concomitant Medications	X		
Tumor Assessment	X Q8 weeks (± 7 days) until PD		Required for subjects who did not progress on study treatment, eg, discontinued for AEs.
NANO scale	X	X	Completed by study physician with each MRI (± 7 days)
Cogstate		X	Cogstate Assessments should occur at Months 6, 12, 18, and 24 (± 15 days) and then continue every 12 months (± 15 days) as long as MRIs are performed. See Section 5.7.1 .
Biomarker Sample	X		Serum and whole blood at time of progression; See Section 5.6 .
Tumor Sample at time of progression	X	X	If biopsy or surgical resection is performed at the time of progression or suspected progression, a tumor biopsy sample (block or slides) should be submitted for central neuropathologic review.
EORTC QLQ-C30 and BN20	X		
EQ-5D	X	X	May be obtained through telephone call or clinic visit
Survival Status		X	Every 3 months (± 14 days) (clinic visit or telephone contact), during Survival phase, include documentation of subsequent chemotherapy.

- ^a Subjects must be followed for at least 100 days after last dose of study treatment. Follow-up visit #1 (FU1) occurs approximately 35 days (± 7 days) after the last dose or coinciding with the date of discontinuation (± 7 days) if date of discontinuation is greater than 30 days after last dose. Follow-up visit #2 (FU2) occurs approximately 115 days (± 7 days) after the last dose

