6 STUDY PERIODS, TREATMENT REGIMENS AND POPULATIONS FOR ANALYSES

6.1 Study Periods

- Baseline period:
 - Baseline evaluations or events will be defined as evaluations or events that occur before the date and time of the first dose of study treatment. Evaluations (laboratory tests, pulse oximetry and vital signs) on the same date and time of the first dose of study treatment will be considered as baseline evaluations.
 - In cases where the time (onset time of event or evaluation time and dosing time) is missing or not collected, the following definitions will apply:
 - ◆ Pre-treatment AEs will be defined as AEs with an onset date prior to but not including the day of the first dose of study treatment
 - ◆ Baseline evaluations (laboratory tests, pulse oximetry and vital signs) will be defined as evaluations with a date on or prior to the day of first dose of study treatment
 - If there are multiple valid assessments on or prior to the first dose of study treatment:
 - ◆ For laboratory tests, the latest non missing labs value on or before first dose date (and time if collected) will be used as the baseline in the analyses. For 'LIPASE' and 'GLUCOSE', for treated subjects only, the last predose assessment with non-missing toxicity grade will be considered as baseline. If multiple assessments exist with the same collection date (and time if collected) and entry date and time, then the first observation is used as baseline.

- 
- 
- 
- Post baseline period:
 - On-treatment AEs will be defined as AEs with an onset date and time on or after the date and time of the first dose of study treatment (or with an onset date on or after the day of first dose of study treatment if time is not collected or is missing). For subjects who are off study treatment, AEs will be included if event occurred within a safety window of 30 days (or 100 days depending on the analysis) after the last dose of study treatment. No “subtracting rule” will be applied when an AE occurs both pre-treatment and post-treatment with the same preferred term and grade.
 - On-treatment evaluations (laboratory tests, pulse oximetry and vital signs) will be defined as evaluations taken after the day (and time, if collected and not missing) of first dose of study treatment. For subjects who are off study treatment, evaluations should be within a safety window of 30 days (or 100 days depending on the analysis) after the last dose of study treatment.

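### Worst-grade laboratory tables compare arms with different scheduled sampling: chemistry is drawn more often on nivolumab, blood counts on temozolomide

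*SAP*

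**What the plan says.** SAP 7.1.2 (Laboratory Tests) covers hematology, serum chemistry and electrolytes. Unless otherwise specified, "subjects will be counted only once for each lab parameter according to their worst on treatment CTC grade".

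Protocol Table 5.1-2 sets the sampling. Its three columns are radiotherapy plus temozolomide, temozolomide maintenance, and radiotherapy plus nivolumab:

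- Chemistry: "Chemistry panel Q4 wks Day 1 each cycle Within 3 days prior to each dose".
- Blood count: "CBC with Differential Weekly Day1&22 of each cycle Within 3 days prior to each dose".

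The table has no column for the 4-week break between radiotherapy and temozolomide maintenance. Nivolumab is given every 2 weeks for 8 doses and then every 4 weeks, "with dose 9 (starting week 17, in the absence of delays") (Protocol 4.5.1.1). Daily temozolomide with radiotherapy runs "typically for 42 days and with a maximum of 49 days" (Protocol 4.5.2.1).

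SAP 6.1 counts a laboratory result as on-treatment only if it is taken after the first dose, so the draw before dose 1 is baseline. After treatment stops, "evaluations should be within a safety window of 30 days (or 100 days depending on the analysis) after the last dose of study treatment".

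**The concern.** The maximum over more draws can only be equal or higher. If two arms have the same true rate of a transient abnormality but one is sampled twice as often, the worst-grade table will show more of it in that arm. Here the schedule itself sets the difference, and it differs by panel. SAP 7.1.1 gives adverse events a rate per 100 person-years; the visible text gives laboratory results no counterpart and no allowance for the number of draws.

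What is at stake is the descriptive reading of liver, renal, electrolyte and hematologic abnormalities by arm. Part of any difference could come from the visit calendar and not from the drug.

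**Working it through.** **Calendar check.** Day 1 is the first dose; assume no delays. Dose 9 of nivolumab falls on day 1 + 8 × 14 = 113, and (113 − 1)/7 + 1 = week 17. This reproduces the protocol's figure, so the 2-weekly period covers days 1–112.

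**Scheduled draw days (Protocol Table 5.1-2).**
- Nivolumab, both panels: 1, 15, 29, 43, 57, 71, 85, 99, then 113, 141, 169 and so on.
- Temozolomide chemistry, 6-week radiotherapy: 1, 29, then maintenance day 1 at 42 + 28 + 1 = 71, then 99, 127, 155 and so on.
- Temozolomide chemistry, 7-week radiotherapy: 1, 29, 78, 106, 134 and so on. If 4-weekly draws continue through the break, add day 57 in either case.
- Temozolomide blood count, 6-week radiotherapy: 1, 8, 15, 22, 29, 36, 71, 92, 99, 120, 127 and so on. With 7 weeks: 1, 8, 15, 22, 29, 36, 43, 78, 99, 106, 127 and so on.

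**Draws counted as on-treatment, days 2–112.**

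| Panel | Nivolumab | Temozolomide |
|---|---|---|
| Chemistry | 7 | 3 (4 with a break draw) |
| Blood count | 7 | 8 (6-week RT) or 9 (7-week RT) |

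The chemistry ratio is 7/3 = 2.3, or 7/4 = 1.75 with a break draw. From week 17, while maintenance lasts, both arms have one chemistry draw per 4 weeks.

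**Chance that a scheduled draw catches a chemistry abnormality.** The documents give no durations, so a duration D is assumed. Onset s is uniform over days 2–112 (111 days). An episode is caught if some draw day d satisfies s ≤ d < s + D, and d may fall after day 112.

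- D = 7. Nivolumab: seven draws each catch 7 onset days and the day-113 draw catches 6, so 55/111 = 50%. Temozolomide: 3 × 7 = 21/111 = 19%, or 4 × 7 = 28/111 = 25% with a break draw.
- D = 14. Nivolumab: 111/111 = 100%. Temozolomide: 42/111 = 38%, or 56/111 = 50%.
- D = 28. Nivolumab: 100%. Temozolomide, 6-week radiotherapy: 3 × 28 + 13 (from the day-127 draw) = 97/111 = 87%. With 7 weeks: 3 × 28 + 6 (from the day-134 draw) = 90/111 = 81%. With a break draw: 100%.

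**Blood counts.** The extra temozolomide draws are clustered in radiotherapy and maintenance, so their effect depends on period and duration.
- Days 2–112, D = 7: nivolumab 50%; temozolomide 8 × 7 = 56/111 = 50% or 9 × 7 = 63/111 = 57%.
- Days 2–112, D = 14: nivolumab 100%; temozolomide 76/111 = 68% or 77/111 = 69%, because no count is scheduled in the break.
- From week 17, per 28 days (nivolumab one draw, temozolomide Days 1 and 22): 7/28 = 25% against 14/28 = 50% for D = 7, and 14/28 = 50% against (14 + 7)/28 = 75% for D = 14.

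**Follow-up visit 1 and the window.** The visit is allowed on days 28–42 after last dose, which is 15 days. A 30-day window keeps 3 of 15 (20%); a 100-day window keeps 15 of 15.

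**The case against.** A reader might infer that the whole safety comparison is tilted against nivolumab. The documents do not support that. The same table draws blood counts more often on temozolomide, so any sampling effect is specific to the panel and can run either way. Abnormalities lasting about 4 weeks or more are caught almost equally. Table 5.1-2 also allows additional clinically indicated tests, which narrow the gap, and the visible SAP text plans no hypothesis test on laboratory grades. All of this stands, and it limits the point to short-lived abnormalities in descriptive tables.

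A reader might also infer that the plan discards the laboratory tests at follow-up visit 1 ("CBC w/differential, LFTs, BUN, creatinine and TSH at 35 days"), since most permitted days fall after day 30. That inference fails. SAP 6.1 also names a 100-day window, which keeps every visit from day 28 to day 42. The window that each laboratory table uses cannot be seen, because most of the SAP's safety section is blacked out. The rule is the same in both arms, so it does not by itself create a difference between them. Stretching the short window to day 42 would still miss some visits: Protocol Table 5.1-3 lets this visit coincide with a discontinuation date more than 30 days after last dose.

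Finally, exact common visit days run out. After day 99 the chemistry schedules are 14 days out of phase (temozolomide day 127 against nivolumab days 113 and 141), and 7-week radiotherapy moves days 71 and 99 to 78 and 106. This is a fair objection to a table built on exact days, and it is why the remedy uses windows.

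**Conclusion.** The point holds as a minor one about reporting. Up to day 112 the worst-grade rule is applied to 7 scheduled on-treatment chemistry draws on nivolumab and 3 or 4 on temozolomide. At equal true rates, a 14-day chemistry abnormality would be caught by scheduled draws in 100% against 38–50% of cases. The gap shrinks to 100% against about 81–100% at 28 days. For hematology the draw count favors temozolomide (8 or 9 against 7). That can make brief abnormalities look more frequent there, most clearly from week 17, although over days 2–112 a 14-day abnormality is caught less often on temozolomide because of the break.

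These figures rest on no dose delays, scheduled draws only, uniform onset and assumed durations. They show what the calendar alone can do and do not predict the observed difference.

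**What to change.** In SAP 7.1.2, keep the all-data worst-grade tables and add supplementary ones by arm, chemistry and hematology separately, limited to a matched sampling schedule:

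- **Chemistry.** One scheduled draw per subject in each prespecified post-baseline window around days 29, 71 and 99, then one per 4-week window. Windows of days 26–32, 68–78 and 96–106, then 28-day windows from day 110, would hold one scheduled draw per arm under either radiotherapy length. The 3-day lead allows for nivolumab draws taken "Within 3 days prior to each dose".
- **Hematology.** The same approach, with a window around day 15 added, when both arms have a count. Where temozolomide has two counts in a window, state in advance which one is used.
- **Both panels.** Report the number of draws per subject by arm, and the number of subjects contributing to each window.

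No change to the SAP 6.1 safety window is needed for this point.

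The cost is two supplementary tables and a count of draws, all from data already collected. The downside is that the matched tables use fewer draws and will miss some real abnormalities, so they supplement the all-data tables and do not replace them.

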7.2 Study Conduct

7.2.1 Accrual

The accrual pattern will be summarized per country, investigational site, and per month for all enrolled and randomized subjects. By subject listing of randomization date, first dosing date, country, investigational site will be provided.

7.2.2 Relevant Protocol Deviations

The following programmable deviations will be considered as relevant protocol deviations and summarized by treatment group for all randomized subjects. Non-programmable relevant eligibility and on-treatment protocol deviations, as well as significant (both programmable and non-programmable) eligibility and on-treatment protocol deviations will be reported through ClinSIGHT listings.

At Entrance:

- Subjects receiving prior treatment for GBM other than Surgery
- Subjects with unknown or methylated MGMT status (using central lab)
- Subjects with KPS < 70

- Subjects with start of treatment more than 52 days after surgery.
- Subjects without baseline MRI scan

On-study:

- Subjects receiving anti-cancer therapy other than study therapy while on study therapy
- Subjects treated different than as randomized

Listings will also be provided.

7.3 Study Population

Unless otherwise specified, the following analyses will be presented by treatment group as “randomized” for all randomized subjects.

7.3.1 Subject Disposition

The total number of subjects enrolled (randomized or not randomized) will be presented along with the reason for not being randomized. This analysis will be performed on the all enrolled subjects population only.

Number of subjects randomized but not treated along with the reason will be tabulated by treatment group as randomized.

Number of subjects who discontinued study treatment along with corresponding reason will be tabulated by treatment group as treated. Reason for discontinuation will be derived from subject status CRF page. This analysis will be performed only on the all treated subjects population.

A subject listing for all treated subjects will be provided showing the subject’s off treatment date and whether the subject continue in the treatment period along with the reason for going off treatment period. A subject listing for all enrolled subjects will also be provided, showing the subject’s race, gender, age, consent date and reason for not being randomized (for those who were not randomized).

